There is lack of prospective studies comparing the above obesity surgical procedures and their effects on food preferences, satiety, gut hormones, bile acids and hepatic glucose output. There is no data on incretin therapies and food preferences in humans [16].

2. Study Objectives

The objective of this study is to investigate the effects of obesity surgical procedures and incretin therapies on food preferences, satiety, gut hormones, bile acids and hepatic glucose output in overweight and obese patients.

3. Study Design

This is a prospective observational controlled trial. 400 overweight and/or obese patients (Body Mass Index $\geq 30 \text{ Kg/m}^2$) will be recruited from the Imperial College NHS Trust, Royal Surrey County Hospital, Musgrove Park Hospital, King's College Hospital and private obesity and/or Diabetes clinics and studied prospectively for 1 year. The study groups will be as follows (n=50 per group):

- Group A: Patients due to undergo gastric bypass
- Group B: Patients due to undergo gastric banding
- Group C: Patients due to undergo sleeve gastrectomy
- Group D: Patients due to undergo endoscopic EndobARRIER insertion
- Group E: Patients due to be commenced on Exenatide
- Group F: Patients due to be commenced on Liraglutide
- Group G (control): Patients due to be commenced on a lifestyle intervention programme
- Group H (control): Patients due to have non bariatric surgery (i.e. cholecystectomy) or an elective diagnostic endoscopy

As part of routine care these patients will be seen by a qualified doctor or dietitian/nutritionist/diabetes specialist nurse (DSN) before and after intervention. Patients in control group G and H will be asked to use a low calorie diet either as part of their routine care or for research purposes only. Patients will be asked to prospectively complete food diaries on three consecutive days which are representative of their usual dietary intake and have a dietary assessment. This assessment will take 30-45 minutes and will take the form of a short discussion of dietary habits and will include completion of eating behaviour questionnaires (assessing dietary/personality traits including restraint, disinhibition, external eating and emotional eating). The first dietary assessment will be completed before the intervention and at 1 month, 3 months, 6 months and 12 months after intervention. Total energy intake and macronutrient composition comparisons pre and post intervention will form the basis of our analysis.

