3.1 Study outcome measures

Primary Endpoint

The primary outcome measure will be total energy intake and dietary composition in terms macronutrient proportions (fat, saturated fat, carbohydrates, sugars, fibre, protein and salt).

Secondary outcomes

The secondary outcome measures will be the ratings of hunger and satiety, gut hormones, bile acid and lipid levels before and after a standardised meal. In the clamp studies, the outcome will also be hepatic glucose output and insulin resistance.

4. Participant Entry

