5.3.2 Serious AEs

An SAE form should be completed and faxed to the Chief Investigator within 24 hours. However, relapse and death due to non-obesity or diabetes related causes, and hospitalisations for elective treatment of a pre-existing condition do not need reporting as SAEs. All SAEs should be reported to the Charing Cross Hospital REC where in the opinion of the Chief Investigator, the event was:

- 'related', i.e. resulted from the administration of any of the research procedures; and
- 'unexpected', i.e. an event that is not listed in the protocol as an expected occurrence

Reports of related and unexpected SAEs should be submitted within 15 days of the Chief Investigator becoming aware of the event, using the NRES SAE form for non-IMP studies. Local investigators should report any SAEs as required by their Local Research Ethics Committee, Sponsor and/or Research & Development Office.

Contact details for reporting SAEs

[contact], attention [name] [name]

Please send SAE forms to: [name] [name], Imperial Weight Centre, [name].

[contact] (Mon to Fri 09.00 – 17.00)

6. Assessment and Follow Up

Assessment will take place through the use of dietary assessments, standardized meal tests and metabolic clamp tests. The dietary assessments will be completed once before and 1, 3, 6 and 12 months post all interventions. The meal tests will take place once before and 2 days, 7-30 days, 3 and 12 months after intervention. The metabolic study will be performed 4 times: at baseline, within 1-2 weeks of a low calorie diet and within 1-2 weeks after their weight loss treatment, whilst on the same liquid diet. The final study visit will take place 6-12 months after the weight loss treatment whilst patients are on their normal diet.

7. Statistics and Data Analysis

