The groups will be allocated at random and thus the distribution of the data should be similar. A student's t-test will be used to compare the two groups for the primary and secondary end points. Descriptive statistics (proportions, mean, medians, standard errors and ranges) will be computed for all baseline variables with 95% CI using either exact binomial confidence intervals or t-confidence intervals for continuous outcomes (after appropriate transformation of the outcome to symmetry). All tests will be conducted at alpha=0.05. Previous studies investigating the effects of obesity surgery on macronutrient intake have recruited 50 patients per group and had power to detect significant differences. This type of study has never been performed with incretin pharmacotherapies and therefore will serve as a pilot for the investigation of the effects of this treatment intervention. The standardised meal study will have 80% statistical power to detect a difference of 5 pmol/L from the expected mean PYY level of 30 pmol/L when the usual standard deviation is 8 pmol/L, the sample size 20 subjects and the alpha error level 5%. This power calculation has been based on previous published results by the same group. Therefore 20 patients in each group are needed.

For the metabolic study, the endpoint is the minimum endogenous glucose production rate. Based on the HOMA-IR results from the only published study on patients having undergone the Endobarrier procedure, we will have a power of 81% at a p level of <0.05 if 6 patients complete the study. To allow for patients dropping out, a maximum of 10 patients will be enrolled to ensure 6 patients complete the study.

8. Regulatory Issues

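### Section 3 rests the analysis on each patient's change from before to after treatment, but the only test in Section 7 is a two-group t-test, which does not fit that comparison

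*Combined protocol and SAP*

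**What the plan says.** Section 3 (Study Design) states the comparison of interest: "Total energy intake and macronutrient composition comparisons pre and post intervention will form the basis of our analysis". Section 3.1 defines the endpoint: "The primary outcome measure will be total energy intake and dietary composition in terms macronutrient proportions". It gives no time point and does not say whether the endpoint is a level or a change. Section 6 sets the schedule: "The dietary assessments will be completed once before and 1, 3, 6 and 12 months post all interventions". Each patient therefore contributes one baseline and four follow-up assessments. There are eight groups, A to H, with 50 patients planned in each.

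Section 7 (Statistics and Data Analysis) gives the only hypothesis test: "A student's t-test will be used to compare the two groups for the primary and secondary end points". It does not say which two of the eight groups are meant, whether follow-up values or changes are tested, or at which visit. The t-based confidence intervals it mentions are for baseline variables. The 50 per group is justified by precedent: "Previous studies investigating the effects of obesity surgery on macronutrient intake have recruited 50 patients per group and had power to detect significant differences". For the meal study it claims "80% statistical power to detect a difference of 5 pmol/L from the expected mean PYY level of 30 pmol/L", with SD 8 pmol/L and 20 subjects.

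**The concern.** Values before and after treatment come from the same patients and are likely to be correlated. A test that compares two groups treats its two sets of values as independent. The comparison that Section 3 makes central therefore has no stated method, and the one stated method addresses a different comparison or ignores the pairing.

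At stake are the precision of the primary result and the freedom left to the analyst. With four follow-up visits, eight groups and an undefined test variable, the choice could be made after the data are seen. The same sentence covers the secondary endpoints, so the meal and clamp outcomes are affected too. The point does not depend on confounding or on multiplicity: it would remain with one endpoint and perfect randomisation.

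**Working it through.** **1. The plan's own figure (meal study, PYY).** Inputs from Section 7: difference 5, SD 8, n = 20, alpha 5% (two-sided assumed). Standardised difference: 5/8 = 0.625.

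- One-sample or paired, normal formula: power = Φ(0.625 × √20 − 1.96) = Φ(2.795 − 1.96) = 79.8%. This reproduces the stated 80%. The exact one-sample t version gives 75.5%.
- Two groups of 20, normal formula: Φ(0.625 × √10 − 1.96) = Φ(1.976 − 1.96) = 50.7%. The exact two-sample t-test gives 48.7% and needs 42 per group for 80%.

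The stated 80% thus belongs to a one-sample or within-patient test, not to the two-group test named in the same section. If the test is paired, 8 must be the SD of the within-patient differences. The protocol does not say whether it is that or the SD of single values.

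**2. Primary endpoint.** The documents give no SD, effect size or before-after correlation (ρ), so the following figures are illustrations. Assumptions: ρ = 0.3, 0.5 or 0.7; equal SDs before and after; normal data; two-sided alpha 0.05; 50 patients per group.

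*Reading A: before and after values of the same patients tested as independent samples.* The true variance of the mean change is 2σ²(1 − ρ)/n, while the two-sample formula uses 2σ²/n. The standard error is therefore too large by 1/√(1 − ρ). Paired power uses the one-sample t with effect 0.4/√(2(1 − ρ)). The type I error comes from simulation (20,000 repetitions).

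| ρ | SE too large by | Actual type I error (nominal 5%) | Power for 0.4 SD change, independent-samples test | Power, paired test |
|---|---|---|---|---|
| 0.3 | 1.20 | about 2% | 51% | 65% |
| 0.5 | 1.41 | about 0.8% | 51% | 79% |
| 0.7 | 1.83 | about 0.06% | 51% | 95% |

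*Reading B: two separate arms compared.* Simulated type I error at ρ = 0.3 and 0.7 is 4.8% on follow-up values and 4.9% on change scores, so standard errors are valid. What differs is precision. Power for an assumed 0.5 SD difference, 50 per arm, uses the two-sample t with effect 0.5 (follow-up values), 0.5/√(2(1 − ρ)) (change scores) or 0.5/√(1 − ρ²) (baseline as covariate).

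| ρ | Follow-up values only | Change scores | Baseline as covariate |
|---|---|---|---|
| 0.3 | 70% | 55% | 74% |
| 0.5 | 70% | 70% | 82% |
| 0.7 | 70% | 89% | 93% |

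Change scores beat follow-up values only when ρ exceeds 0.5. Baseline adjustment gains whenever ρ is not zero. On either choice, a contrast between arms does not report the change within a group.

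**The case against.** The strongest reply is that Section 7 is under-specified rather than wrong. It does not use the word unpaired, and a paired t-test is also a Student's t-test. The meal-study figure, which works only as a one-sample or paired calculation, suggests that the authors had a within-patient test in mind for at least that endpoint. The preceding sentence in Section 7 speaks of allocating groups, so the two groups most naturally means treatment arms, and a t-test between arms has valid standard errors. Even on the worst reading the error is conservative: it costs power and creates no excess of false positives.

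Most of this stands. A reader might infer that the error bars on the primary endpoint will be wrong and that power will be lost. The documents do not support either as a flat statement. The first holds only if before and after values are tested as independent samples, which no section says. The second depends on a correlation and a test variable that are not given. Nor do the documents describe separate tests at each visit, so the plan cannot be said to discard visits or the patients missing at one.

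The reply does not supply the missing method. On every reading, either the named test does not answer Section 3's question or its wording must be changed before it does.

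A further caution concerns the remedy. The power gain from a baseline covariate assumes equal expected baselines. Section 3 forms the groups from patients already due for a given treatment, so baseline adjustment and change scores may estimate different things, and neither removes confounding.

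**Conclusion.** The mismatch between Sections 3 and 7 is real and should be corrected before analysis. That part rests on the text alone. The meal-study arithmetic supports it without any assumed correlation: 79.8% by a one-sample or paired formula, against about 49% with the two-group t-test at 20 per group. It concerns a secondary endpoint.

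The consequences for the primary endpoint are conditional. The inflation of 1.20 to 1.83 and the fall from 65–95% to 51% power apply only if before and after values are treated as independent. The gain from 70% to 74–93% applies only if arms would otherwise be compared on follow-up values alone. All rest on assumed correlations of 0.3 to 0.7 and assumed effects of 0.4 and 0.5 SD.

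**What to change.** Replace the t-test sentence in Section 7 with:

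- **Within each group:** the mean change from the patient's own baseline at each visit, with a paired 95% confidence interval and paired t-test.
- **Between named groups, dietary outcomes:** one model per outcome on all post-treatment visits, with group, visit, group-by-visit, baseline value and a random patient effect. Name the group comparisons and the visit of main interest. Report unadjusted change scores as a sensitivity analysis, because the groups consist of patients already due for a treatment.
- **Clamp study:** paired change from baseline only. Six planned completers are too few for the model above.
- **Meal study:** state which comparison the 80% refers to, and whether 8 pmol/L is the SD of single values or of within-patient differences.

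The baseline and repeat assessments are already scheduled. The cost is new wording in Section 7 and slightly more analysis work, with no new data or patients.

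### The unadjusted t-test rests on random allocation that the design section contradicts, so differences in site mix can pass as treatment effects and the 5% error rate is not guaranteed

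*Combined protocol and SAP*

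**What the plan says.** Section 3 (Study Design) opens with "This is a prospective observational controlled trial". Its 400 patients are "recruited from the Imperial College NHS Trust, Royal Surrey County Hospital, Musgrove Park Hospital, King's College Hospital and private obesity and/or Diabetes clinics". The eight groups of 50 are defined by treatment already planned, for example "Group A: Patients due to undergo gastric bypass". The section sets no site quota, matching or stratification, and does not say which sites supply which groups.

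Section 7 (Statistics and Data Analysis) says the opposite about how groups arise: "The groups will be allocated at random and thus the distribution of the data should be similar". The next sentence names the only between-group test: "A student's t-test will be used to compare the two groups for the primary and secondary end points". Alpha is 0.05. Neither section mentions a site term, clustering or any covariate.

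The primary outcome (Section 3.1) is total energy intake and macronutrient composition. It comes from patient-completed food diaries and a discussion-based dietary assessment. Section 3 makes comparison before and after intervention the basis of the analysis. It adds that, in routine care, "these patients will be seen by a qualified doctor or dietitian/nutritionist/diabetes specialist nurse (DSN) before and after intervention".

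**The concern.** The randomisation sentence is the only support Section 7 offers for comparing groups without adjustment, and Section 3 does not describe a randomised design. Without randomisation or stratification, nothing in the plan makes the groups similar in where their patients come from.

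Site could matter for this outcome. Dietary support and the conduct of dietary assessments may differ between hospitals and private clinics. That is an inference from the setting; the documents do not report it.

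If two groups have different site mixes and sites differ in the change in intake, part of the site difference enters the group contrast. The t-test has no term to separate the two, and its standard error treats the 100 patients in a contrast as independent. The plan would print a p-value even for two groups that share no site.

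**Working it through.** **Plan's own figure.** There is none to reproduce. The 50 per group rests on precedent, with no effect size, SD or power. The 80% power in Section 7 belongs to the 20-patient meal study and does not bear on this point.

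**Inputs from the documents.** 50 per group; alpha 0.05 (taken as two-sided); Student's t-test; four named hospitals plus private clinics.

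**Assumptions.** 5 sites; normal data; total variance 1; intraclass correlation ρ = 0.01 to 0.10, meaning the share of variance in the analysed quantity that lies between sites; and the site layouts below.

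**Step 1: true variance of the contrast.** Let d be the difference between the two groups in the share of patients from each site. Then V = ρ·Σd² + (1 − ρ)·2/50.

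**Step 2: variance the t-test estimates.** With p the site shares within a group, E = [(1 − ρ) + ρ(1 − Σp²)·50/49]·2/50.

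**Step 3: false-positive rate.** With q = V/E, the rate is about 2·P(T₉₈ > 1.984/√q).

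Worked case, 20/15/10/5/0 against 0/5/10/15/20 at ρ = 0.05:
- d = 0.4, 0.2, 0, −0.2, −0.4, so Σd² = 0.40; Σp² = 0.16 + 0.09 + 0.04 + 0.01 = 0.30.
- V = 0.05 × 0.40 + 0.95 × 0.04 = 0.058.
- E = (0.95 + 0.05 × 0.70 × 50/49) × 0.04 = 0.0394.
- q = 1.47; 1.984/√1.47 = 1.64; rate about 10.5%.

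| Layout (reversed in the other group) | Σd² | Σp² | ρ = 0.01 | ρ = 0.05 | ρ = 0.10 |
|---|---|---|---|---|---|
| 10/10/10/10/10 | 0 | 0.20 | 4.9% | 4.5% | 4.1% |
| 20/15/10/5/0 | 0.40 | 0.30 | 6.1% | 10.5% | 15.9% |
| 30/10/10/0/0 | 0.80 | 0.44 | 7.2% | 16.3% | 25.7% |
| One different site each | 2.00 | 1.00 | 10.9% | 30.0% | 44.0% |

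Simulation of the same layouts agrees to within about 0.5 percentage points. At ρ = 0 the rate is about 5% in every layout.

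**Step 4: a check without an intraclass correlation.** Take a fixed gap of 0.2 SD between two sites. The non-centrality is gap × difference in site share ÷ √(2/50). With a 20-point difference in share it is 0.2 × 0.2/0.2 = 0.2, giving 5.5%. With full confounding it is 0.2 × 1/0.2 = 1.0, giving 16.8%.

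**Step 5: what a site term does and costs.** In simulation, a linear model with fixed site terms gives 4.8% to 5.5% wherever the groups share a site. Its information on the group contrast is Σ nₐn_b/(nₐ + n_b), summed over sites, against 25 for 50 versus 50 with no site term. Power below is for a 0.566 SD effect (about 80% with independent data) at ρ = 0.05.
- Even: information 25; SE = √(0.95/25) = 0.195; power about 82%.
- 20/15/10/5/0: 3.75 + 5 + 3.75 = 12.5, so variance doubles; SE = √(0.95/12.5) = 0.276; 0.566/0.276 = 2.05; power about 53%.
- 30/10/10/0/0: one shared site, information 5, so variance is five times larger; SE = √(0.95/5) = 0.436; 0.566/0.436 = 1.30; power about 25%.
- One different site each: information 0; treatment and site cannot be separated.

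Step 5 leaves out any gain from adjusting for baseline intake, because the documents give no correlation between baseline and follow-up.

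**The case against.** The strongest reply is that inflation needs two things together: different site mixes and site differences in the analysed outcome. The documents give figures for neither. With equal mixes the t-test is at or slightly below 5%, which is harmless. Milder imbalance than the layouts above (30/30/20/10/10% against its reverse) at an intraclass correlation of 0.01 to 0.02 gave only 5.2% to 5.6% in simulation. Nothing in Section 3 says that any group comes from a single site. This stands. A reader might infer that the 5% rate is definitely broken, or that the standard errors are materially wrong whatever the mix; the documents support neither reading.

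Second, the analysis is based on change from before to after intervention, and a within-patient change cancels stable site differences such as local diet or case mix. This also stands. It limits the concern to site differences in change, for example through different dietetic support after the intervention. It does not remove it.

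Third, if groups really were allocated at random, site would not bias the t-test. That defence depends on the Section 7 sentence that Section 3 contradicts, so it cannot be relied on until the two are reconciled.

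Fourth, site is only one consequence of non-random groups with no adjustment. A site term leaves BMI, diabetes status and indication untouched, and on its own could reassure falsely. This is right, and it is why site should sit in the model beside baseline covariates.

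**Conclusion.** The point holds in conditional form. Section 7 bases an unadjusted test on random allocation, Section 3 describes observational groups formed by planned treatment across several sites, and no other feature of the plan keeps site differences out of the group contrasts. The 5% error rate is therefore not guaranteed.

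The size depends entirely on assumed quantities: the number of sites, the layouts, and the between-site share of variance in the change in intake. The lower end of the range is negligible. The 44% upper end needs both complete separation of the two groups by site and an intraclass correlation of 0.10, so it is a bound on the assumptions tried and not an estimate for this study. The contradiction between the sections and the missing site term need no assumption; both are plain in the text.

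**What to change.** 1. Reconcile Section 7's statement on random allocation with Section 3's design and group definitions.
2. In Section 7, for the 50-per-group diet comparison, replace the t-test with a linear model of post-intervention intake on group, baseline intake and recruiting site, with any other pre-specified baseline covariates. Allow small private clinics to be pooled if sparse, by a rule written in advance.
3. Tabulate group by site.
4. Report contrasts between groups that share few or no sites as descriptive and not separable from site.

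This costs SAP wording, a few degrees of freedom and one table, with no extra patients or procedures. The real price is precision where overlap is low: about 53% power for 0.566 SD in the 20/15/10/5/0 layout and about 25% in the 30/10/10/0/0 layout. In the first of these the t-test shows about 77%, but only with a false-positive rate near 10%, so the two are not like for like.

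I would not extend the site terms to the 20-per-group meal study or to the clamp study planned around 6 completers, where they would be too sparse. Nor would I ask for control recruitment to be spread over sites, since nothing shows that every site can supply those patients. The adjusted model does not remove patient-level confounding by indication, and the report should say so.

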
20 patients in each group will undergo more detailed measurements of food intake, hunger, satiety, gut hormones and bile acids. The research protocol will be the similar to that previously published by the Department of Metabolic Medicine, Imperial College, London. Participants will be fasted for 12 hours overnight and will attend for the study on 5 occasions. On each occasion venous blood samples will be taken and visual analogue scores will be measured over a 3 hour period using previously published methodology (Appendix Table 1: Test Periods). Samples or sample containers will be anonymised before collection but will be traceable back to the individual patients. Urine will be collected once. A qualified medical doctor will insert a venepuncture cannula into the arm of the patient and 5ml blood will be withdrawn at baseline, 15, 30, 60, 90, 120, 150 and 180 minutes following ingestion of a

standard 400kcal meal as below (Appendix Table 2: Protocol of each Test). After each sample the cannula will be flushed with saline to keep it patent. The protocol will be carried out 5 times per patient, pre intervention, 2, 7-30 days, 3 and 6-12 months post intervention. Plasma samples will be analysed for gut hormones as well as for primary bile acids and lipids. An extra blood and urine test will be obtained 1 month after treatment but not followed by a meal test.

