Ten to twenty patients in each group (different from those taking part in the meal studies) will undergo measurements of hepatic glucose output/insulin resistance through euglycaemic hyperinsulinaemic clamps (Metabolic Study). Patients will be studied up to 4 times: at baseline, within 1-2 weeks of a low calorie diet and within 1-2 weeks after their weight loss treatment, whilst on the same liquid diet. The low calorie liquid diet is nutritious and contains all appropriate macronutrients. Such diets are frequently used as part of obesity interventions to reduce weight and risk. Patients will provide the investigators with a detailed food diary of their food consumption for this period. The final study will take place 6-12 months after the weight loss treatment whilst patients are on their normal diet. Throughout this period, the investigators will be in close contact with those patients who have diabetes to optimise their glucose control through adjustments of their glucose-lowering medications. Our unit has a track record in safe and effective glycaemic management before and after weight loss interventions [17].

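### The plan names Student's t-test for between-group comparisons with no stated support for equal variances, so the nominal 5% is not assured where group sizes differ, chiefly in the clamp study

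*Combined protocol and SAP*

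**What the plan says.** Section 7 names one test: "A student's t-test will be used to compare the two groups for the primary and secondary end points". It sets the level for all of them: "All tests will be conducted at alpha=0.05". It gives one reason to expect groups to be alike in distribution: "The groups will be allocated at random and thus the distribution of the data should be similar". It plans no unequal-variance test, variance check or fallback. Transformation to symmetry is mentioned only in the sentence on descriptive statistics for baseline variables.

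Section 3 describes a different design: "This is a prospective observational controlled trial". Its eight groups are defined by the treatment each patient is already due to receive.

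Three statements in Section 3 and one in Section 7 bear on group size:
- Diet study (Section 3): "The study groups will be as follows (n=50 per group".
- Meal study (Section 3): "20 patients in each group will undergo more detailed measurements of food intake, hunger, satiety, gut hormones and bile acids".
- Clamp study (Section 3): "Ten to twenty patients in each group (different from those taking part in the meal studies".
- Clamp study (Section 7): "a maximum of 10 patients will be enrolled to ensure 6 patients complete the study". The text does not say whether this cap is per group or applies only to EndoBarrier patients.

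**The concern.** The pooled t-test estimates one common variance. It keeps its error rate if the true variances are equal, and nearly keeps it if the group sizes are equal. If both differ, the standard error is wrong. It is too small when the smaller group is more variable and too large when the larger group is.

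The plan's only argument for similar distributions is random allocation, which the design does not have. Even randomisation would make only baseline spread alike, not spread after treatments as different as bypass, an incretin drug and a diet programme. The clamp study is the one part whose stated sizes allow unequal groups. At stake is the validity of each single p-value and confidence interval. This is separate from confounding and from the number of tests, and would remain after both were dealt with.

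**Working it through.** **Inputs.** Alpha is 0.05 (Section 7); two-sided is assumed, since sidedness is not stated. Planned sizes are 50 v 50 (diet), 20 v 20 (meal) and 10 to 20 per group (clamp), all from Section 3. Section 7 adds 10 enrolled and 6 completing for the clamp study. No SD by group is given for any endpoint; the only SD is 8 pmol/L for PYY. SD ratios of 1.5 and 2 are therefore assumptions. Data are taken as normal.

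**The plan's own figure.** The plan states no error rate beyond the nominal 0.05. The one power figure with full inputs is 80% for PYY (difference 5, SD 8, n = 20). As a one-sample or paired normal calculation, Φ(5/(8/√20) − 1.96) = Φ(2.795 − 1.96) = 79.8%, which reproduces it. As a two-group calculation with 20 per group, Φ(5/(8√(2/20)) − 1.96) = Φ(0.016) = about 51%. The clamp study's 81% cannot be checked, because no effect size or SD is given.

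**Why the pooled test drifts (10 v 20, SD ratio 2).** The pooled squared standard error averages s_p²(1/n₁ + 1/n₂), with s_p² = [(n₁−1)σ₁² + (n₂−1)σ₂²]/(n₁+n₂−2). The true value is σ₁²/n₁ + σ₂²/n₂.
- Small group more variable (σ₁ = 2, σ₂ = 1): s_p² = (9×4 + 19×1)/28 = 1.964. The pooled value is 1.964 × 0.15 = 0.295, against a true 4/10 + 1/20 = 0.450. The standard error is √(0.295/0.450) = 0.81 of what it should be. The approximate error is 2Φ(−1.96 × 0.81), about 11%.
- Large group more variable (σ₁ = 1, σ₂ = 2): s_p² = (9×1 + 19×4)/28 = 3.036. The pooled value is 0.455, against a true 1/10 + 4/20 = 0.300. The standard error is 1.23 times too large, and the test is conservative.
- Equal sizes n: s_p² × 2/n = (σ₁² + σ₂²)/n, which is the true value. Only a small degrees-of-freedom effect remains.

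**Simulated error at nominal 5%** (no true difference, 1,000,000 runs per scenario). Repeat runs agree to within about 0.2 of a percentage point.

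| Sizes | Small group's SD ×1.5 | Small group's SD ×2 | Large group's SD ×1.5 | Large group's SD ×2 |
|---|---|---|---|---|
| 10 v 20 | 8.6% | 11.4% | 2.7% | 1.9% |
| 6 v 10 | 7.7% | 9.9% | 3.4% | 2.7% |

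With equal variances the pooled test gives 5.0% at both size pairs. With equal sizes and a twofold SD ratio it gives about 5.3% (20 v 20) and 5.1% (50 v 50). Across these cases Welch's test lies between 4.8% and 5.3%.

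**Uneven dropout in the equal-sized studies (SD ratio 2).** At 12 v 20 the error is 9.6% or 2.5%, and at 30 v 50 about 9.3% or 2.4%, depending on which group is more variable. Both assume 40% loss in one group and none in the other. At 18 v 20 or 45 v 50, with the smaller group more variable, it is about 6%.

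**Cost of Welch's test if variances are equal** (pooled power set at 80%): about 78% at 10 v 20, 77% at 6 v 10, 73% at 6 v 20 and 79% at 12 v 20.

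**The case against.** The strongest reply is that the error is hypothetical. It needs unequal sizes and unequal variances together, and the documents establish neither: a permitted range of 10 to 20 does not mean sizes will differ, and no SD by group is given. This stands, so the point must be put conditionally. It also cuts the other way, because the plan's one stated ground for similar distributions is contradicted by its own design.

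A second reply is that the main comparisons may be within patient. Section 3 makes changes in intake from before to after treatment the basis of the analysis, the clamp study measures each patient up to four times, and the 80% power figure matches a paired calculation. For a paired test, pooling across groups does not arise. This also stands, but Section 7 explicitly compares two groups on primary and secondary endpoints, so between-group tests are planned as well.

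A third is that Section 7's cap, if it applies to every group, rules out 10 v 20. That is correct; 6 v 10 completers would then be the extreme, at 7.7 to 9.9%. A 6 v 20 case, where the pooled error at ratio 2 would be 16.7% or 0.8%, takes its sizes from two passages that conflict and should not be used as the headline.

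A fourth is that Section 7 has larger faults, such as a two-group test for eight groups measured repeatedly, and that a proper longitudinal model would need its own variance specification. That is fair, and the fix allows for such a model.

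**Conclusion.** The point holds as a conditional one, worth a cheap improvement. Equal variances have no valid stated support, and where sizes also differ the nominal 5% is not assured. In the clamp study, under assumed SD ratios of 1.5 to 2, the error is about 8.6 to 11.4% (10 v 20) or 7.7 to 9.9% (6 v 10) if the smaller group is more variable. If the larger group is, it is about 1.9 to 2.7% or 2.7 to 3.4%. The direction cannot be known from the documents. The figures assume normal data, a two-sided test and the pooled form that the name Student's usually denotes; the plan does not use the word pooled.

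A reader might infer more than this:
- That the 5% level is actually breached. The documents do not show this, since they give no variances by group.
- That the primary endpoint or the meal study is affected as planned. At their equal sizes the error stays at about 5.0 to 5.3%, and the documents give no dropout figure for either study.
- That false positives generally more than double. In the clamp scenarios above this occurs only at 10 v 20 with a twofold SD ratio.

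**What to change.** In Section 7, replace Student's t-test with Welch's unequal-variance t-test, or a model with group-specific residual variances, for between-group comparisons, and report the matching confidence intervals. State which comparisons are between groups and which are within patient. Remove the random-allocation rationale. Reconcile the clamp group sizes in Sections 3 and 7, saying whether the maximum of 10 is per group.

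The change is a few lines of text and needs no new data. It is not quite free: if variances are in fact equal, power falls from 80% by about 2 points at 10 v 20, 3 at 6 v 10 and 7 at 6 v 20, and by 1 point or less at 12 v 20 or larger. Planning similar clamp group sizes would keep that loss small.
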